#### 5.3.3. Handling of Missing and/or Unquantifiable Immune Response Data

Missing immune response data will not be imputed.

Values below the lower limit of quantification (LLOQ) will be imputed based on the type of analysis:

- Values below LLOQ will be imputed to LLOQ/2, except for the calculation of the geometric mean of the increase from baseline, values below LLOQ will be imputed to LLOQ.
- Data above the ULOQ will be imputed with the ULOQ.

The ULOQ and LLOQ values per assay will be available in the database.

# 5.4. Primary Safety Endpoint Analysis

Safety endpoints include:

- Solicited local (injection site) and systemic AEs for 7 days after vaccination
- Unsolicited AEs for 28 days after vaccination
- Serious adverse events (SAEs) and adverse events of special interest (AESIs) until 6 months after vaccination

No formal statistical testing of safety data is planned. Safety data will be analyzed descriptively by cohort and group. All safety analyses will be based on the FA Set. Continuous variables will be summarized using the following statistics, as appropriate: number of observations, median, minimum and maximum. Frequencies and percentages (one decimal place) will be generated for categorical variables.

Safety data will be analyzed by study intervention regimens as designed per protocol, per phase and across the entire study period where applicable. For unsolicited AE, denominator for the percentages is the number of participants in the considered population and phase for a certain regimen (incidence per 100 participants/phase). For solicited AEs, the denominator for the percentages is the number of participants with data assessed by the PI in the considered population and phase for a certain and phase for a certain regimen (incidence per 100 participants/phase).

# 5.4.1. Adverse Events

# 5.4.1.1. Definitions

Solicited AEs shown in the tables are extracted from the investigator assessment pages (CE) of the CRF. For unsolicited AEs, only the AEs within the 28-day period following each vaccination will be presented in the safety tables except for SAE and potential AESI, which will be captured and tabulated in the outputs covering the whole study period. Unsolicited non-serious adverse events collected outside the 28-day period following the vaccination will be presented through listings.

Solicited administration site symptoms will be by definition considered as related to the study vaccine.

The severity of the AEs will be classified as grade 1 to 4. Solicited events of grade 0, not reported in the CE domain, will therefore not be reported in the AE analysis.

For AESI analyses, the following subcategories are defined:

- Potential AESIs as identified by the investigator
- Potential AESIs selected programmatically Those include all reported AEs that are identified by the selection rule:
  - SMQ (Standardised MedDRA Queries) = "EMBOLIC AND THROMBOTIC EVENTS (SMQ)" or
  - (SUB\_SMQ1 = "HAEMATOPOIETIC THROMBOCYTOPENIA (SMQ)" and SCOPE in ( "BROAD", "NARROW")) or HLT (higher level term)="Thrombocytopenias"
- Potential AESIs qualified for assessment Potential AESIs (programmed/CRF) that have risk levels assessed by one of the following three criteria are considered 'qualified for assessment':
  - Brighton Collaboration Level (Level 1-5)
  - CDC Tier (non-tier 1/2, tier 1, tier 2)
  - PRAC criteria (confirmed, possible, probable, unlikely, criteria not met)

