AEs and special reporting situations, whether serious or non-serious, that are related to study procedures or that are related to non-investigational sponsor products will be reported from the time a signed and dated informed consent form (ICF) is obtained until the end of the study/early withdrawal. Solicited AEs, collected through a participant diary, will be recorded from the time of vaccination until 7 days post-vaccination. All other unsolicited AEs and special reporting situations, whether serious or non-serious, will be reported from the time of vaccination until 28 days post-vaccination. All SAEs, AESIs, and AEs leading to discontinuation from the study (regardless of the causal relationship) are to be reported from the moment of vaccination until completion of the participant's last study-related procedure, which may include contact for safety follow-up. All AEs will be followed until resolution or until clinically stable.

STATISTICAL METHODS

Sample Size Determination

Humoral Immunogenicity Analysis

Immunogenicity assessments will be performed in all participants.

Sample size calculations for the immunogenicity objectives are performed under the following assumptions.

For the humoral immune response in terms of neutralizing antibody GMTs:

- no difference between all adults aged 18 to 59 years (Groups 1 and 3) and adults aged 65 years and older (Group 5) and no difference between high-risk adults aged 18 to 59 years and adults aged 65 years and older (ie, assuming a true GMT ratio of Day 15 [ie, 14 days after vaccination] RSV A2 neutralizing antibody titers equal to 1 for those comparisons, and similar standard deviation)
- a standard deviation of 1.5 at the log₂ scale for VNA A2 on Day 15*
- non-inferiority limit of 0.67 (2/3)
- 1-sided α of 2.5%

For the humoral immune response in terms of neutralizing antibody seroresponse rates (defined as a 4-fold increase from baseline in Day 15 antibody titers):

- Seroresponse rates are assumed to be 85% in all adults aged 18 to 59 years, high risk adults aged 18 to 59 years and adults aged 65 years and older, based on available data from Phase 1/2 clinical studies,
- Non-inferiority margin of 10%
- 1-sided α of 2.5%

In addition:

• a ratio of 1:1:1 for the **active** groups in Cohorts 1, 2, and 3

• hierarchical testing (ie, test first Group 1+3 versus Group 5, if non-inferiority is demonstrated: test Group 3 versus Group 5)

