8.3.1. Time Period and Frequency for Collecting AE, SAE, and AESI Information

All AEs

AEs and special reporting situations, whether serious or non-serious, that are related to study procedures or that are related to non-investigational sponsor products will be reported from the time a signed and dated ICF is obtained until the end of the study/early withdrawal.

Clinically relevant medical events not meeting the above criteria and occurring between signing of ICF and moment of vaccination will be collected on the Medical History eCRF page as pre-existing conditions.

Solicited AEs, collected through a participant diary, will be recorded from the time of vaccination until 7 days post-vaccination.

All other unsolicited AEs and special reporting situations, whether serious or non-serious, will be reported from the time of vaccination until 28 days post-vaccination.

All SAEs and AEs leading to discontinuation from the study (regardless of the causal relationship) are to be reported from the moment of vaccination until completion of the participant's last study-related procedure, which may include contact for safety follow-up. The sponsor will evaluate any safety information that is spontaneously reported by an investigator beyond the time frame specified in the protocol.

See Section 7.2 for procedures associated with withdrawal of consent.

All AEs will be followed until resolution or until clinically stable.

SAEs

All SAEs occurring during the study must be reported to the appropriate sponsor contact person by study-site personnel immediately, but no later than 24 hours of their knowledge of the event.

Information regarding SAEs will be transmitted to the sponsor using the SAE Form and Safety Report Form of the eCRF, which must be completed and reviewed by a physician from the study site, and transmitted to the sponsor immediately, but no later than within 24 hours. The initial and follow-up reports of an SAE should be transmitted electronically or by facsimile (fax). Telephone reporting should be the exception and the reporter should be asked to complete the appropriate form(s) first.

AESIs

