# 5.4.1.2. Analysis of Adverse Events

Number and percentage of participants with at least one particular AE (unsolicited/solicited) will be tabulated. Unsolicited AEs will be summarized by System Organ Class and Preferred Term. Solicited AEs will be summarized by class (administration site, systemic) and preferred term. AESI will be summarized by Interest Category and Preferred Term.

For solicited AEs, the following tables will be provided: summary, by worst severity grade, at least grade 3, related (systemic only), time to onset (in days) and duration (in days). Note: Duration is defined as number of days from the start of the event until resolution of the event. The time to first onset is defined as (date of first onset – reference date + 1). The reference date is the start date of the post-dose period.

For unsolicited AEs following tables will be provided: summary table (including SAE, fatal outcome, AESI, AE leading to study discontinuation), all events, most frequent, at least grade 3, related, AE leading to study discontinuation, related, SAE, and related SAE.

Moreover, table with Covid AEs, potential AESI as identified by the investigator, potential AESIs selected programmatically and potential AESI qualified for assessment will be created.

Potential AESIs selected programmatically will be tabulated by categories: 'Embolic and thrombotic events (SMQ)' and 'Haematopoietic Thrombocytopenia (SMQ) (broad) or HLT = Thrombocytopenias'. Potential AESI determined programmatically, related to study vaccine (investigator assessment), will be tabulated similarly.

Potential AESIs as identified by the investigator, will be tabulated by categories: '*Embolic and thrombotic events (SMQ)*' and '*Haematopoietic Thrombocytopenia (SMQ)* (broad) or HLT = Thrombocytopenias', and 'Other'. Potential AESI as identified by the investigator, related to study vaccine (investigator assessment), will be tabulated similarly.

Potential AESIs qualified for assessment will be tabulated by categories: 'Embolic and thrombotic events (SMQ)' and 'Haematopoietic Thrombocytopenia (SMQ) (broad) or HLT = Thrombocytopenias'

All AESI analyses will be presented by phase as well as by time interval. The definition of the different time intervals can be found in Section 5.1.2.

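### The SAP's table of AEs leading to study discontinuation omits late-onset events that are neither serious nor potential AESIs, although the protocol collects them to study end

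*SAP*

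**What the plan says.** **Collection.** Protocol 8.3.1 puts AEs leading to discontinuation on the same footing as SAEs: "All SAEs and AEs leading to discontinuation from the study (regardless of the causal relationship) are to be reported from the moment of vaccination", and onwards "until completion of the participant's last study-related procedure, which may include contact for safety follow-up". The synopsis has the same rule and adds AESIs: "All SAEs, AESIs, and AEs leading to discontinuation from the study (regardless of the causal relationship". Other unsolicited AEs are collected for 28 days only.

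**Tabulation.** SAP 5.4.1.1 says that, for unsolicited events, "only the AEs within the 28-day period following each vaccination will be presented in the safety tables except for SAE and potential AESI". The exception runs over the whole study: "except for SAE and potential AESI, which will be captured and tabulated in the outputs covering the whole study period". The next sentence deals with the remainder: "Unsolicited non-serious adverse events collected outside the 28-day period following the vaccination will be presented through listings".

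**Planned outputs.** SAP 5.4.1.2 lists a "summary table (including SAE, fatal outcome, AESI, AE leading to study discontinuation", among other rows. Its separate tables include "at least grade 3, related, AE leading to study discontinuation, related, SAE, and related SAE". SAP 5.2 also tabulates reasons for termination throughout the study.

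**Other relevant text.** Protocol 9.4.4 builds the AE analysis on events with onset up to 28 days plus all SAEs and AESIs, and leaves output on later AEs optional. SAP 5.4.1.2 also provides listings and/or narratives, as appropriate, for participants who discontinue because of an AE.

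**The concern.** For ordinary unsolicited AEs a 28-day table is sensible, because routine collection also stops at 28 days. AEs leading to discontinuation differ: sites must report them to the end of follow-up, so nothing in data collection calls for cutting the table short. The SAP's exception names two of the three categories that the protocol synopsis follows to the end and leaves out the third.

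Two consequences follow for someone reading the report. First, the discontinuation count by group can be lower than the number of AE-related withdrawals in the disposition table, and the SAP gives no rule to reconcile them. Second, the discontinuation row of the summary table mixes two windows: the whole study for events that are serious or potential AESIs, and 28 days for all others. The neighbouring SAE and AESI rows cover the whole study.

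**Working it through.** The plan states no figure to reproduce. The check is a reading of the texts against each other, plus simple arithmetic on the time window.

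**Which events are affected.** An AE leading to study discontinuation is missing from the table only if all three conditions hold:

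1. *It starts after the post-dose period.* SAP 5.4.1.3 allocates AEs by start date, not by date of withdrawal. An AE that starts on Day 20 and leads to withdrawal on Day 90 is inside the window. One that starts on Day 60 is outside it. The same section also merges a later event into the post-dose period when it overlaps or directly follows an event there with the same preferred term.
2. *It is not an SAE.* SAEs are exempt from the limit throughout the study.
3. *It is not a potential AESI.* These are exempt too. Under Protocol 8.3.6.1, thrombocytopenia and the thrombotic events in Appendix 9 count as potential AESIs.

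Events meeting all three conditions go to listings under SAP 5.4.1.1, with narratives as appropriate under SAP 5.4.1.2.

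**Does other text bring them back?** SAP 5.4 says that safety data are analysed by phase and, where applicable, over the entire study. That is a general statement. SAP 5.4.1.1 is specific, lists its exceptions and assigns the remainder to listings, so it governs. Protocol 9.5 describes the final analysis as adding SAE data to study end and does not mention this category.

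**Length of the uncovered period.** Inputs: last visit at Day 183 (Protocol 4.4); 28-day window (SAP 5.4.1.1); Day 29 visit with a window of ±5 days (Protocol 1.3); post-dose period ending at the later of 28 days and the 28-day visit (SAP 5.1.2, Table 3).

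- Follow-up after vaccination: 183 − 1 = 182 days.
- Outside a 28-day window: 182 − 28 = 154 days; 154/182 = 84.6%.
- Outside if the 28-day visit is 5 days late: 182 − 33 = 149 days; 149/182 = 81.9%.

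**Weight of one omitted participant**, using the planned group sizes in Protocol 4.1, Table 1:

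- Active groups (1, 3, 5): 1/315 = 0.3 percentage points.
- Placebo Groups 2 and 4: 1/70 = 1.4 points.
- Placebo Group 6: 1/28 = 3.6 points.

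These figures show what a single case would change. They do not predict how many cases there will be.

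**The case against.** The best defence is that the SAP does what the protocol's analysis section asks. Protocol 9.4.4 covers AEs with onset up to 28 days plus all SAEs and AESIs, and makes anything later optional. AEs leading to discontinuation are not an endpoint, and collecting data to study end does not oblige anyone to tabulate them. This stands: a reader might infer that the SAP breaches the protocol, and it does not. But the same section permits later summaries, so nothing there prevents the change.

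Nor are the events lost. Listings hold them, narratives may describe them, and the disposition table counts the withdrawals. That also stands, but a listing gives no rate by group, and the listing and narrative provision for discontinuations is worded as and/or and as appropriate.

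The importance should also be kept in proportion. This is a single-injection study, and Protocol 7.1 notes that vaccination can be discontinued only before it is given. Withdrawal from follow-up months later says less about tolerability than stopping a continuing treatment would.

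Finally, table layouts are in a separate data presentation specifications document that is not available here. A reader might infer that the report will give no warning of the different windows. The SAP specifies none, but the table specifications might.

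**Conclusion.** The point holds in a narrow form. The planned discontinuation table and summary row omit AEs that start after the 28-day post-dose period, lead to withdrawal, and are neither serious nor potential AESIs. The protocol requires those events to be collected, so the count by group can be too low and can disagree with the disposition table.

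Three stronger readings are tempting and not supported. The row does not stop at Day 28 for every event, because SAEs and potential AESIs are exempt. A participant who withdraws late is not necessarily missing, because the start date of the AE decides. The 85% of days outside the window does not mean that 85% of events are missed, because the timing and number of events are unknown.

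The conclusion assumes that the specific rule in SAP 5.4.1.1 prevails over the general sentence in SAP 5.4, and that the unseen table specifications do not already widen the table. The importance is modest: no primary immunogenicity result is affected, and the number of omitted events may be zero.

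**What to change.** In SAP 5.4.1.1, extend the exception so that it covers SAEs, potential AESIs and AEs leading to study discontinuation. In SAP 5.4.1.2, present the discontinuation table and the matching summary row for the whole study, split by post-dose and follow-up phase. Add a check of the count against the AE-related reasons for termination in the disposition table, with any difference explained.

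The cost is one phrase in the SAP, an adjusted table shell and a reconciliation step. The data are already collected, and because Protocol 9.4.4 allows later summaries, the change appears to need no protocol amendment. If the 28-day limit is kept on purpose, the table and row should at least state which period applies to which events.

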# 5.4.1.2. Analysis of Adverse Events

Number and percentage of participants with at least one particular AE (unsolicited/solicited) will be tabulated. Unsolicited AEs will be summarized by System Organ Class and Preferred Term. Solicited AEs will be summarized by class (administration site, systemic) and preferred term. AESI will be summarized by Interest Category and Preferred Term.

For solicited AEs, the following tables will be provided: summary, by worst severity grade, at least grade 3, related (systemic only), time to onset (in days) and duration (in days). Note: Duration is defined as number of days from the start of the event until resolution of the event. The time to first onset is defined as (date of first onset – reference date + 1). The reference date is the start date of the post-dose period.

For unsolicited AEs following tables will be provided: summary table (including SAE, fatal outcome, AESI, AE leading to study discontinuation), all events, most frequent, at least grade 3, related, AE leading to study discontinuation, related, SAE, and related SAE.

Moreover, table with Covid AEs, potential AESI as identified by the investigator, potential AESIs selected programmatically and potential AESI qualified for assessment will be created.

Potential AESIs selected programmatically will be tabulated by categories: 'Embolic and thrombotic events (SMQ)' and 'Haematopoietic Thrombocytopenia (SMQ) (broad) or HLT = Thrombocytopenias'. Potential AESI determined programmatically, related to study vaccine (investigator assessment), will be tabulated similarly.

Potential AESIs as identified by the investigator, will be tabulated by categories: '*Embolic and thrombotic events (SMQ)*' and '*Haematopoietic Thrombocytopenia (SMQ)* (broad) or HLT = Thrombocytopenias', and 'Other'. Potential AESI as identified by the investigator, related to study vaccine (investigator assessment), will be tabulated similarly.

Potential AESIs qualified for assessment will be tabulated by categories: 'Embolic and thrombotic events (SMQ)' and 'Haematopoietic Thrombocytopenia (SMQ) (broad) or HLT = Thrombocytopenias'

All AESI analyses will be presented by phase as well as by time interval. The definition of the different time intervals can be found in Section 5.1.2.

For AESI analyses, attribution to the intervals will be done similarly to the unsolicited AEs as described in Section 5.4.1.3. For Step 2 of phase allocation of adverse events, the '0 - 28 days post-dose' interval should be treated similar to 'active' periods and the rest as 'non- active' periods.

Listings and/or participant narratives will be provided as appropriate, for those participants who die, discontinue study due to an AE, or experience a severe or serious AE or potential AESI.

# 5.4.1.3. Phase Allocation of Adverse Events

As the analysis of solicited events will be based on the overall assessment of the investigator, which is documented in the CE domain, the ADAM (Analysis Data Model) dataset will be based on the CE domain. Solicited events are allocated to the phases as described below, however they are always allocated to the post-dose period and will never be attributed to the screening phase. Time of day is not considered while attributing solicited AEs to phases.

For unsolicited AEs, the steps below are followed as well.

#### **Step 1: Allocation of events to the periods:**

Adverse events in the SDTM database are allocated to periods based on their start date/time. If the start date/time of an event falls between (or on) the start and stop date/time of a period, the AE is attributed to that period (treatment-emergent principle).

- In case of partial start or stop dates (ie time and/or day and/or month and/or year missing), the events are allocated to the periods using the available partial information on start and end date; no imputation will be done. If, for instance, the AE start date only month and year are available, these data are compared to the month and year information of the periods. This rule may lead to multiplication of the event as a consequence of its assignment to multiple periods.
- In case of a completely missing end date, the date is imputed by the cut-off date of the analysis for participants still ongoing in the study, and by the end date of the last period for participants who discontinued or completed the trial. The imputed end dates will not be shown in the data listings. In case of a completely missing start date, the event is allocated to the first active phase (Post-dose period), except if the end date of the AE falls before the start of the first active phase (Post-dose period).

#### **Step 2: Combination of events:**

Overlapping/consecutive events are defined as events of the same participant with the same preferred term which have at least 1 day overlap or for which the start date of an event is 1 day after the end date of the preceding event. Overlapping/consecutive events may be combined into one AE or not, according to the following rules:

1) If overlapping/consecutive events start in one of the following phases/periods - Screening or Follow-up (defined as non-active periods) - followed by an AE in - Post-dose period (defined as active period) - they are allocated to their respective phases/periods and are considered as separate events.

2) In case overlapping/consecutive events start within a single period, they are considered as one and the same AE. The individual events which contribute to this AE are retained as individual records in the ADaM database but are assigned the same onset, period, and total duration. All related attributes to the AE/phase/period should also be consistent with the new event.

3) In case overlapping/consecutive events start in both an active period followed by a consecutive non-active period, they are allocated to the active period only and are considered as one and the same AE. The individual events which contribute to this AE are retained as individual records in the ADaM database but are assigned the same onset, treatment period, and total duration. All related attributes to the AE/phase/period should also be consistent with the new event.

4) In case an active period is followed by another active period, and the overlapping/consecutive events start in both periods, they are allocated to their respective period and are considered as separate AEs. In case overlapping/consecutive events start in non-consecutive periods (regardless of active or non-active), they are allocated to their respective period and are considered as separate AEs.

5) In case a non-active period is followed by another non-active period, and the overlapping/consecutive events start in both periods, they are allocated to the first period and they are considered as one and the same AE. The individual events which contribute to this AE are retained as individual records in the ADaM database but are assigned the same onset, period, and total duration. All related attributes to the AE/phase/period should also be consistent with the new event.

Remarks:

1. Events can only be combined into one and the same AE if their start and stop dates are known.

2. In case the completely missing end date is imputed (for period allocation), this date is also considered as a complete date.

3. Time is not considered when determining overlap of events.

